7.3.2 Dose modifications due to non-hematologic related adverse events

Dose modifications for non-hematologic toxicities should be based on toxicities occurring during the previous cycle. For toxicities that lead to a dose reduction, the dose will not be re-escalated during subsequent cycles.

Any patient who develops a Grade 3 or 4 non-hematologic toxicity that does not resolve to \leq Grade 1 within 28 days should be discontinued from the study treatment. However, if the Investigator determines that the non-hematologic toxicity was due to one study drug and not the other, treatment with the remaining study drug may continue as clinically appropriate.

Based upon the maximum non-hematologic toxicities experienced during the previous cycle, dose adjustments for subsequent cycles are to be made according to the criteria defined in [Appendix B Table 9](#) (unless specified per unique toxicities as noted below).

Appendix B Table 9 Non-hematologic toxicity dose modification and management

Electrocardiogram QT corrected interval prolonged		
QTc Value	CBDP	AZD1775
QTc 450-480 ms (males) or 470-480 (females)	No dose modifications	Hold. Once QTc interval has returned to pretreatment status and correction of possible electrolyte imbalance has been made, resume at next lower dose level.
QTc 481-500 ms	No dose modifications	Hold. Seek cardiologist advice.

QTc \geq 501 ms	Discontinue treatment	Discontinue treatment
Shift from baseline of \geq 60ms	Discontinue treatment	Discontinue treatment
<hr/>		
CTCAE version 4.03	CBDP	AZD1775
Grade 0 - 2	No dose modification	No dose modification
Grade 3 ^{b,c,d}	Hold ^a	Hold ^a
Grade 4 ^b	Hold until toxicity resolves to Grade \leq 1. Resume with 1 dose level reduction	Hold until toxicity resolves to Grade \leq 1. Resume with 1 dose level reduction
Second repeat incidence of Grade 3 or 4 toxicity (except nausea, vomiting, fatigue, malaise, lethargy, anorexia, alopecia)	Discontinue treatment	Discontinue treatment
<hr/>		
Hepatic		
<hr/>		
CTCAE v4.03	CBDP	AZD1775
Grade 1-2	No dose modification	No dose modification
Grade 3 or 4 (manifested as elevations in ALT, AST, ALP, or bilirubin)	Hold until resolves to Grade \leq 1 or baseline, then resume CBDP with a 1 level dose reduction. If not resolved within 28 days, discontinue CBDP.	Hold until resolves to Grade \leq 1 or baseline, then resume study drug with a 1 level dose reduction. If not resolved within 28 days, discontinue study drug.
<hr/>		
Diarrhea or mucositis		
<hr/>		
CTCAE v4.03	CBDP	AZD1775
Grade 1-2	No dose modification	No dose modification
Grade 3 or 4 (or requiring hospitalization)	Hold ^a	Hold ^a
<hr/>		
Nephrotoxicity		
<hr/>		
CTCAE v4.03	CBDP	AZD1775
Grade 0-1	No dose modification	No dose modification

Grade ≥ 2 Hold until resolves to Grade ≤ 1 or Hold^a
baseline, then resume CBDP with
a 1 level dose reduction. If not
resolved within 28 days,
discontinue CBDP.

Neurotoxicity		
CTCAE v4.03	CBDP	AZD1775
Grade 1	No dose modification	No dose modification
Grade 2	Hold until toxicity resolves to Grade ≤ 1 . Resume with 1 dose level reduction.	No dose modification
Grade 3 or 4	Discontinue treatment	Discontinue treatment

- ^a Hold until toxicity resolves to \leq Grade 1 and then resume at the same dose with no modification.
- ^b Dose reduction for nausea and vomiting should be made only if Grade 3 or Grade 4 toxicity occurs in spite of maximum anti-emetics.
- ^c For a Grade 3 pulmonary embolism, the dose should be held but the subsequent doses do not have to be reduced 1 dose level, at the Investigator's discretion.
- ^d Grade 3 electrolyte value(s) (ie, hypokalaemia) do not require a dose reduction once the electrolyte is \leq Grade 1.

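### Arm B, Appendix B Table 9: the general Grade 3 row resumes both drugs at the same dose, but footnote b on that row provides for a reduction for nausea and vomiting, and footnotes c and d leave the default unclear

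*Protocol*

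**What the plan says.** Section 7.3.2 of Appendix B makes Table 9 the governing rule: "dose adjustments for subsequent cycles are to be made according to the criteria defined in" that table, apart from toxicities given their own instructions.

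The general part of the table (the block graded by CTCAE, after the QTc block) has these entries:

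- **Grade 3 row, both drugs:** hold, with footnote a. Footnote a says to wait for Grade 1 or lower "and then resume at the same dose with no modification". The Grade 3 label also carries footnotes b, c and d.
- **Grade 4 row, both drugs:** hold until Grade 1 or lower, then "Resume with 1 dose level reduction". This label carries footnote b only.
- **Footnote b:** "Dose reduction for nausea and vomiting should be made only if Grade 3 or Grade 4 toxicity occurs in spite of maximum anti-emetics".
- **Footnote c:** "For a Grade 3 pulmonary embolism, the dose should be held but the subsequent doses do not have to be reduced 1 dose level". It leaves the choice to the investigator.
- **Footnote d:** Grade 3 electrolyte values "do not require a dose reduction once the electrolyte is" back to Grade 1 or lower.

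QTc, hepatic, diarrhea/mucositis, renal and neurological toxicity have separate rows. The diarrhea/mucositis row ("Grade 3 or 4 (or requiring hospitalization") uses footnote a, and footnotes b to d are not attached to it.

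**The concern.** Footnote a rules out any reduction after a Grade 3 event, while footnote b names Grade 3 among the grades at which a reduction is made. For Grade 3 vomiting despite maximum anti-emetics, one site can follow footnote a and restart at full dose; another can follow footnote b and restart one level down. Both would be following the table.

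Footnotes c and d add a second difficulty. They are attached to Grade 3 and not to Grade 4, yet Grade 4 is the general row that prescribes a reduction. A waiver normally implies a rule being waived, and the Grade 3 row contains none.

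The stakes are mainly patient safety and consistency of dosing between sites. Section 7.3.2 bars re-escalation after a reduction, and Section 7.3.1 says the same, so the choice made at one restart carries through all later cycles. The table's discontinuation rule for a second Grade 3 or 4 event excepts nausea and vomiting, so the disputed row can apply to the same patient more than once.

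**Working it through.** No sample size, error rate or event count is involved. The check sets the Grade 3 row beside each footnote, then sizes the difference.

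**1. What the table prescribes after a Grade 3 event resolves**

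| Grade 3 event | Row with footnote a | Other footnote | Result |
|---|---|---|---|
| Nausea/vomiting despite maximum anti-emetics | same dose | b: reduction | contradictory |
| Nausea/vomiting without maximum anti-emetics | same dose | b: no reduction | consistent |
| Pulmonary embolism | same dose | c: reduction not obligatory | a gives the outcome that c permits; c redundant |
| Electrolytes | same dose | d: no reduction required | agree; d redundant |
| Any other event under the general row | same dose | none, but c and d imply a reduction that can be waived | default unclear |
| QTc, hepatic, diarrhea/mucositis, renal, neurological | own rows | b to d not attached | not affected |

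The phrase in footnote c, "the subsequent doses do not have to be reduced 1 dose level", identifies the implied reduction as one level.

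**2. Whether other text settles it**

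- Section 7.3 allows reductions or holds as the treating physician sees fit. It does not say whether footnote a or footnote b applies.
- Section 7.3.2 excepts unique toxicities, but Section 7.3.3.3 on nausea and vomiting covers anti-emetics and gives no dose consequence.
- Section 7.3.3.1 links adjustment of AZD1775 to weight monitoring and gives no restart rule.

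**3. Size of one dose level** (Appendix B Tables 6 and 7)

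- AZD1775: 175/225 = 0.778, about 22% lower. Over five doses per cycle, 5 × 225 = 1125 mg against 5 × 175 = 875 mg.
- Carboplatin: 4/5 = 0.80, so a 20% lower target AUC.

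**4. How many patients, at most roughly**

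Appendix B Section 2.4.2 reports Grade 3 or higher events among 59 patients given AZD1775 with paclitaxel and carboplatin. The printed percentages reproduce: vomiting 6/59 = 10.2%, nausea 3/59 = 5.1%. For Appendix B's figure of up to 20 patients:

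- vomiting: 20 × 6/59 = 2.0
- nausea: 20 × 3/59 = 1.0

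These counts include any Grade 4 events, for which the table does state a reduction level, and are not limited to failure of maximum anti-emetics. The same patient may appear in both counts.

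**The case against.** The best defence is that a footnote naming a toxicity is an ordinary way to write an exception to a row. On that view footnote b overrides footnote a for nausea and vomiting. Its wording can also be taken as a limiting condition: it says when a reduction may be considered and does not order one. Footnotes c and d can likewise be read as guidance on the physician's general freedom to reduce under Section 7.3, with no hidden default of one level.

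Part of this stands. Footnotes c and d produce no contradictory dose for the events they name, and the argument that they imply a default reduction is an inference.

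The defence does not remove the conflict over footnote b. As a limit on the Grade 4 row it makes sense, but it also names Grade 3, where footnote a leaves no reduction to limit. If it is an override, it does not say which drug is reduced or by how many levels at Grade 3. Nothing in the document says that the footnote takes precedence.

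A reader might go further and infer that the restart dose is contradictory for the commonest serious non-haematological events. The document does not support that. Diarrhea, which ties with vomiting at 6/59, has its own row and is outside the conflict. The figures concern CTCAE grade, and master protocol Section 7.3.3 separates severity from seriousness.

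**Conclusion.** The point holds in a limited form. The direct contradiction is confined to Grade 3 nausea or vomiting despite maximum anti-emetics, and it concerns both drugs. For other Grade 3 events under the general row, the stated rule is the same dose, but footnotes c and d cast doubt on it.

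The difference is one dose level per drug and is permanent once taken. The counts of about 2 and 1 in 20 are rough upper figures. They assume that rates from a paclitaxel triplet in platinum-sensitive ovarian cancer carry over to Arm B, where Section 7.3.3.3 requires a 5-HT3 antagonist before each AZD1775 dose and adds dexamethasone unless contraindicated or not tolerated.

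It might also be inferred that the ambiguity blurs what Arm B's response rate describes. The effect there is minor: few patients are likely to be involved, and master protocol Section 9.5.4 has exposure, delays and dose reductions summarised, so the doses given will be visible. The reason to correct the table is that a dosing instruction bearing on safety contradicts itself.

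**What to change.** Reconcile the general Grade 3 row and footnotes a to d of Appendix B Table 9 so that, for each drug, they state one consistent consequence after resolution. For nausea and vomiting, the text should say which instruction prevails and, if any reduction is meant, which drug and how many levels it concerns. Footnotes c and d should either refer to a rule that the row contains or stop referring to a reduction. The sponsor decides which consequence applies; this review takes no view on the dose.

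The cost is revised table and footnote wording and a letter to sites. No extra patients, visits or procedures are needed.

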7.3.3 Non-hematologic toxicity management guidelines

7.3.3.1 Gastrointestinal system disorders

Gastrointestinal AEs including nausea, vomiting, and diarrhea have previously been associated with AZD1775 treatment. These types of toxicities observed in AZD1775 studies are not unexpected for therapies that include full-dose chemotherapy. Patients should therefore be closely monitored for signs of gastrointestinal AEs and, if necessary, they should be managed clinically with supportive treatment not limited to anti-emetics, IV hydration, and anti-diarrheal treatment as needed. Weight should be carefully monitored with other vital signs and doses of AZD1775 adjusted accordingly.

Following the receipt of 3 SAEs of gastrointestinal haemorrhagic events from ongoing studies, this topic has been identified as a new important potential risk to be kept under close surveillance with immediate attention given to any case report received events.

7.3.3.2 Diarrhea

Due to frequent reports of diarrhea with AZD1775 administration, vigorous anti-diarrheal treatment loperamide (Imodium®) is required at the first onset of diarrhea, according to the American Society of Clinical Oncology guidelines. Oral loperamide 4 mg should be administered every 2 hours until diarrhea-free for at least 12 hours. The first dose of

loperamide could be lowered to 2mg if the diarrhoea is recurrent and if, in the opinion of the treating physician, the diarrhoea is not severe.

Patients should be instructed to notify the Investigator or research staff of the occurrence of bloody or black stools, symptoms of dehydration, fever, inability to take liquids by mouth, and inability to control diarrhea within 24 hours of using loperamide or other prescribed anti-diarrhoeal medications.

If diarrhea is severe (ie, requiring IV rehydration) and/or associated with fever or severe neutropenia (Grade 3 or 4), broad-spectrum antibiotics must be prescribed. Patients with severe diarrhea or any diarrhea associated with severe nausea or vomiting should be hospitalised for IV hydration and correction of electrolyte imbalances.

7.3.3.3 Nausea and vomiting

All patients must receive a 5-HT₃ antagonist, ondansetron (ZOFTRAN[®]) 8 mg PO BID or granisetron (KYTRIL[®]) 1 mg PO BID prior to each dose of AZD1775. Additional doses of 5-HT₃ antagonist may be used if needed. In addition, dexamethasone 4 mg PO will be given with each AZD1775 dose, unless contraindicated or not well-tolerated. Dexamethasone may be continued on further days of dosing, potentially at a lower dose. Dexamethasone or the 5-HT₃ antagonist may be given by IV. Promethazine (PHENERGAN[®]), prochlorperazine (COMPAZINE[®]), and benzodiazepine may still be used as additional adjunctive treatments during AZD1775 therapy. **Please note: aprepitant [E Mend] and fosaprepitant are not permitted due to known DDIs.**

Patients should be strongly encouraged to maintain liberal oral fluid intake.

Suitable alternative medications may be used, with adequate justification, in those studies where the use of any of the above medications might interfere with other study procedures or are deemed insufficient.

7.3.3.4 Motor neuropathy or muscle weakness

Any onset of Grade >2 motor neuropathy or Grade >2 muscle weakness should be evaluated by an electromyogram to rule out the possibility of chronic inflammatory demyelinating polyneuropathy (CIDP). With a diagnosis of CIDP, the patient should be discontinued from study treatment.

7.3.3.5 Dose modifications for infusion reactions

Infusion reactions (eg, rash, urticaria, erythema, pruritus, bronchospasm, and hypotension) can occur with the agents used in this study. There is increased risk of a reaction with CBDP. CBDP must be discontinued in patients experiencing a Grade 3 or 4 infusion reaction during treatment.

To identify the grade of a reaction, refer to the list below adapted from the General Disorders and Administration Site Conditions section of the NCI CTCAE version 4.03:

- Grade 1: Mild transient reaction; infusion interruption not indicated; intervention not indicated
- Grade 2: Therapy or infusion interruption indicated but responds promptly to symptomatic treatment (eg, antihistamines, nonsteroidal anti-inflammatory drugs, narcotics, IV fluids indicated for ≤ 24 hours)
- Grade 3: Prolonged (eg, not rapidly responsive to symptomatic mediation and/or brief interruption of infusion); recurrence of symptoms following initial improvement; hospitalization indicated for other clinical sequelae. Any infusion that is interrupted and not resumed within the visit will be considered a Grade 3 reaction.
- Grade 4: Life-threatening consequences; urgent intervention indicated

7.3.3.6 QTc prolongation

The QTc interval will be measured in 12-lead ECGs at baseline and at the commencement of each treatment cycle; and an assessment made of the emergence, if any, of QTc prolongation. Serum electrolyte levels should be obtained at baseline and at commencement of each treatment cycle.

Checking and correction of abnormal electrolyte levels and renal function are advised, especially in case of diarrhoea.

The administration of AZD1775 with substances known to prolong the ECG QTc interval is not recommended.

Special note: The potential risk of concomitant use of AZD1775 with ondansetron (known to prolong the QTc interval) should be taken into account.

Dose modifications or discontinuations for patients experiencing QTc prolongations are summarized in [Appendix B Table](#) above.

8. INVESTIGATIONAL PRODUCT AND OTHER TREATMENTS

8.1 Identity of investigational product(s)

Investigational product	Dosage form and strength
AZD1775	25 mg or 100 mg capsules
CBDP ^a	IV sourced locally

^a Under certain circumstances when local sourcing is not feasible, standard of care treatment may be supplied centrally through AstraZeneca

8.1.1 AZD1775

AstraZeneca will supply AZD1775 capsules for oral use. The capsules will be supplied at 2 strengths (100 and 25 mg) in high-density polyethylene bottles, which sufficiently protects the drug from light. The different capsule strengths should not be combined in the same bottle at any time. Additional information about the IP may be found in the IB.

AZD1775 225 mg is taken PO in approximately 12-hour intervals BID over 2.5 days on Days 1 to 3 of each treatment cycle. Treatment cycles are every 21 days. AZD1775 should be taken with 8 ounces of water approximately 2 hours before or 2 hours after food. All patients must take a 5-HT3 antagonist prior to each dose of AZD1775, for example, ondansetron 8 mg PO BID or granisetron 1 mg PO BID. The 5-HT3 antagonist may be given by IV if necessary.

If a patient misses 1 of the 2 daily doses according to schedule, the dose should be taken as soon as possible, but not more than 6 hours after the missed dose was scheduled. If greater than 6 hours, the missed dose should be skipped, and the patient should take the next dose when scheduled.

If vomiting occurs after a patient takes the AZD1775 dose, the patient should be instructed not to retake the dose but to wait until the next scheduled dose of AZD1775. If no dose is scheduled for the following day, the dose will not be 'made up'. If vomiting persists, the patient should contact the Investigator.

8.1.2 Carboplatin

Area under the Curve (AUC) 5 IV Day 1 every 21 days

CBDP, at a dose calculated to produce an AUC of 5, will be administered by IV infusion according to institutional standards.

The CBDP dose will be calculated using the Calvert formula based on the patient's GFR, which is estimated by using the CrCl.

Calvert formula: CBDP dose (mg) = target AUC × (GFR + 25)

The Food and Drug Administration (FDA) has recommended that physicians consider capping the dose of CBDP for the desired exposure (AUC) to avoid potential toxicity due to overdosing for all laboratories using the isotope dilution mass spectrometry derived serum creatinine measurements. Therefore, the maximum dose of CBDP should be based on a CrCl no greater than 125 mL/min for patients with normal renal function. In these, CBDP can be safely dosed according to the instructions in the drug's labelling. Refer to the US FDA, Center for Drug Evaluation and Research website (<http://www.fda.gov/AboutFDA/CentersOffices/OfficeofMedicalProductsandTobacco/CDER/ucm228974.htm>) for more specific guidelines.

Cockcroft-Gault formula:

$$\text{CrCl (GFR)} = \frac{[(140 - \text{age}) \times (\text{wt. in kg})] \times (0.85 \text{ if female})}{(72 \times \text{serum creatinine [mg/dL]})}$$

Patients may receive prophylactic anti-emetic therapy for moderately emetogenic chemotherapy according to institutional standards, excluding aprepitant Emend.

[figure not shown]
Refer to the CBDP package insert for additional information.

8.2 Dose and treatment regimens

For Arm B, up to 20 eligible patients will be enrolled, and all patients will receive:

AZD1775 225 mg BID PO for 2.5 days from Day 1 + CBDP AUC 5 Day 1 IV; q3w until PD

Appendix B Figure 2 AZD1775 + carboplatin therapy dosing schedule

AZD1775 should be administered first, then followed by carboplatin infusion.

8.3 Labeling

Please refer to Section 8.3 of the master protocol for details regarding labelling applicable to all arms.

8.4 Storage

Please see Section 8.4 of the master protocol.

8.5 Compliance

AZD1775 dosing compliance will be reviewed with the patient at the beginning of each new treatment cycle when AZD1775 is dispensed. All patients will be required to complete a dosing diary, which must be returned to the clinic for review at each visit. The patient should be instructed to record each date and time the dose(s) was taken in the dosing diary. If a dose

is missed, the reason must be noted in the diary. A copy of the dosing diary is provided in the study reference materials.

Patients should be advised to return any unused AZD1775 in the original bottles, in addition to returning any empty bottles.

The administration of all study drugs (including IPs) should be recorded in the appropriate sections of the case report form (CRF).

8.6 Accountability

Please see Section 8.6 of the master protocol.

8.7 Concomitant and other treatments

Please refer to Section 8.7 of the master protocol for details regarding concomitant and other treatments applicable to all arms. Details regarding concomitant and other treatments applicable to Arm B are described below.

8.7.1 Prohibited concomitant medications

- No formal clinical drug interaction studies have been performed with AZD1775. An exploratory assessment of the effect of aprepitant on AZD1775 exposure in oncology patients suggests that there is a drug interaction between AZD1775 and aprepitant, as exposure to AZD1775 increased by ~60% when aprepitant was coadministered with AZD1775. The observed increase in AZD1775 exposure is likely the result of CYP3A4 inhibition by aprepitant. This increase in exposure is statistically significant. At the selected MTD, this increase may also be of clinical importance. Therefore, concomitant treatment with aprepitant and fosaprepitant is not allowable per protocol until further evaluation.
- Potent or moderate inhibitors or inducers of CYP3A4, sensitive CYP3A4 substrates, and CYP3A4 substrates with a narrow therapeutic window should be avoided until additional data on drug-drug interaction becomes available. The use of sensitive substrates of CYP3A4, such as atorvastatin, simvastatin and lovastatin, is prohibited in this study. As grapefruit and Seville oranges are known to contain moderate inhibitors of CYP3A4, these fruits or their products (including marmalade, juice, etc.) should be avoided while taking AZD1775.
- *In vitro* data suggests that AZD1775 may also be a weak reversible inhibitor of CYP2C19. Caution should be exercised with concomitant administration of AZD1775 and agents that are sensitive substrates of CYP2C19, or substrates of this enzyme with narrow therapeutic range; refer to [Appendix I](#) for a list of sensitive substrates of CYP2C19, or substrates of this enzyme with narrow therapeutic range.

- AZD1775 has been shown to be a weak inducer of CYP1A2 *in vitro* with a maximum measured response between donors of 39.9% to 93.1% (at 10 μ M) and 18.6% to 32.5% (at 5 μ M) of the positive control omeprazole (50 μ M), respectively. Given the nature of the AZD1775 dosing schedule, however, the risk of induction in the clinic is considered low. No specific precautions are recommended at this time, except to be initially vigilant when using substrates of CYP1A2 with a narrow therapeutic range.
- *In vitro* studies have shown that AZD1775 may be a substrate and inhibitor for human P glycoprotein (P-gp). Caution should be exercised when agents that are inhibitors or substrates of P-gp are administered concomitantly with AZD1775 (see Appendix I).
- Recent *in vitro* transporter studies have shown AZD1775 to be an inhibitor of breast cancer resistance protein (BCRP) [median inhibition concentration 5.1 μ M]. This finding is particularly relevant for drugs administered PO where exposure is normally limited by BCRP-mediated efflux, in particular some statins. Modeling has predicted a substantial increase in the exposure of atorvastatin when co-administered with AZD1775, and the use of atorvastatin is therefore prohibited in the current study. Other drugs where the disposition is mediated via BCRP should be administered with caution, dose modification considered, or substituted by an alternative drug.
- Metformin should be used with caution. AZD1775 has been shown to be an inhibitor of multi-antimicrobial extrusion protein (MATE) 1 and MATE2K transporters. A drug interaction with substrates of either transporter cannot be ruled out, the most important substrate known to date being metformin.
- Herbal preparations/medications are not allowed throughout the study. These herbal medications include, but are not limited to: St. John's wort, kava, ephedra (ma huang), ginkgo biloba, dehydroepiandrosterone, yohimbe, saw palmetto, and ginseng. Patients should stop using these herbal medications 7 days prior to first dose of AZD1775.
- Avoid concomitant use of strong CYP3A inhibitors and moderate CYP3A inhibitors: azole antifungals (ketoconazole itraconazole, fluconazole, and voriconazole), macrolide antibiotics (erythromycin and clarithromycin), cimetidine, HIV protease inhibitors, and nefazodone
- Avoid concomitant use of strong CYP3A inducers and moderate CYP3A inducers: phenytoin, barbiturates, and rifampicin

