13. Patient has had prescription or non-prescription drugs or other products known to be sensitive to cytochrome P450 (CYP)3A4 substrates or CYP3A4 substrates with a narrow therapeutic index, or to be moderate to strong inhibitors/inducers of CYP3A4 which cannot be discontinued 2 weeks prior to the first day of study drug dosing and withheld throughout the study until 2 weeks after the last dose of study drug. Coadministration of aprepitant or fosaprepitant during this study is prohibited. The use of sensitive substrates of CYP3A4, such as atorvastatin, simvastatin and lovastatin, is also prohibited in this study. As grapefruit and Seville oranges are known to contain moderate inhibitors of CYP3A4, these fruits or their products (including marmalade, juice, etc.) should be avoided while taking AZD1775. (see Appendix I Disallowed Medications and Medications to be Administered with Caution). Transporter studies (in vitro) have shown that AZD1775 is an inhibitor of breast cancer resistance protein (BRCP). The use of rosuvastatin in this study is prohibited.
14. Herbal preparations are not allowed throughout the study. These herbal medications include but are not limited to: St. John's wort, kava, ephedra (ma hung), ginkgo biloba, dehydroepiandrosterone (DHEA), yohimbe, saw palmetto and ginseng. Patients should stop using these herbal medications 7 days prior to first dose of study treatment.
15. Patients with Grade ≥ 2 neuropathy will be evaluated on a case-by-case basis after consultation with AstraZeneca Study Physician.
16. Patient with mean resting corrected QT interval (specifically QTc calculated using the Fridericia formula) > 470 msec from 3 ECGs performed within 5 minutes apart at study entry or congenital long QT syndrome.
17. Any of the following cardiac diseases currently or within the last 6 months as defined by New York Heart Association \geq Class 2 ([Appendix B1 New York Heart Association Criteria](#))
18.).
 - Unstable angina pectoris
 - Congestive heart failure
 - Acute myocardial infarction
 - Conduction abnormality not controlled with pacemaker or medication
 - Significant ventricular or supraventricular arrhythmias (patients with chronic rate-controlled atrial fibrillation in the absence of other cardiac abnormalities are eligible)
18. AZD1775 should not be given to patients who have a history of Torsades de pointes unless all risk factors that contributed to Torsades have been corrected (see Section

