Appendix I BCRP Substrates

Daunorubicin	Doxorubicin	Rosuvastatin
Sulfasalazine	Topotecan	

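### Arm B: exclusion criterion 13 prohibits rosuvastatin because AZD1775 inhibits BCRP, but section 8.7.1 never names it and places BCRP-mediated drugs other than atorvastatin under caution

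*Protocol*

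**What the plan says.** Three places in the protocol bear on statins in Arm B.

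- **Appendix B section 4.2, exclusion criterion 13.** After the CYP3A4 restrictions, the criterion reports in vitro transporter work showing that AZD1775 inhibits BCRP (printed there as BRCP), and then states: "The use of rosuvastatin in this study is prohibited".
- **Appendix B section 8.7.1.** The CYP3A4 bullet reads: "The use of sensitive substrates of CYP3A4, such as atorvastatin, simvastatin and lovastatin, is prohibited in this study". A separate bullet takes up the BCRP finding, says it matters for oral drugs and some statins in particular, reports modelling of atorvastatin exposure, and concludes "and the use of atorvastatin is therefore prohibited in the current study". It then gives a general rule for the rest of the class: "Other drugs where the disposition is mediated via BCRP should be administered with caution, dose modification considered, or substituted by an alternative drug".
- **Appendix I, BCRP Substrates.** The table has five entries, one of them "Rosuvastatin". Nothing marks any entry as prohibited or as caution only.

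Rosuvastatin is mentioned in criterion 13 and in the Appendix I table, and nowhere else in the protocol.

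**The concern.** One pharmacological finding leads to two different rules. Criterion 13 derives from it a prohibition on rosuvastatin. Section 8.7.1 derives from it a prohibition on atorvastatin and a caution rule for everything else handled by BCRP. Appendix I puts rosuvastatin in that remaining class.

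Two things are at stake. First, safety: the protocol itself treats raised exposure to oral BCRP substrates as a real possibility, and a patient could be given, in good faith, a drug that another section forbids. Second, consistency of the deviation record: whether rosuvastatin use is logged as a deviation would depend on which section the site or monitor consulted. Section 9.5 of the master protocol allows an optional sensitivity analysis of efficacy in patients without important protocol deviations, so the deviation record has at least one possible analytic use.

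**Working it through.** No formula applies. The check is a comparison of the text, statin by statin.

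| Statin | Criterion 13 (Appendix B 4.2) | Section 8.7.1 | Appendix I |
|---|---|---|---|
| Atorvastatin | Prohibited (CYP3A4) | Prohibited twice: CYP3A4 bullet and BCRP bullet | CYP3A4 substrate; not in the BCRP table |
| Simvastatin | Prohibited (CYP3A4) | Prohibited (CYP3A4 bullet) | CYP3A4 substrate |
| Lovastatin | Prohibited (CYP3A4) | Prohibited (CYP3A4 bullet) | CYP3A4 substrate |
| Rosuvastatin | Prohibited (BCRP) | Not named; the general BCRP clause would cover it | BCRP substrate |

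1. For atorvastatin, simvastatin and lovastatin, criterion 13 and 8.7.1 agree on status. Atorvastatin carries two different reasons.
2. For rosuvastatin the status depends on the route taken. Criterion 13 gives prohibited. Section 8.7.1 read with the Appendix I table gives caution, dose modification or substitution.
3. The gap is specific to rosuvastatin. The other products named in criterion 13 (aprepitant, fosaprepitant, the three other statins, grapefruit and Seville orange) all reappear in 8.7.1. Rosuvastatin is the one not carried across, which looks more like a drafting slip than a deliberate distinction.
4. No cross-reference closes the gap. Master protocol section 8.7 sends sites to the arm appendix for restricted, prohibited and permitted medication, and the part of Appendix B under that heading is 8.7. Section 8.7.1 does not point back to criterion 13. Section 8.7.4 then leaves medication not already described to the Investigator's discretion, so an omission from 8.7 has practical weight.

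**The case against.** The strongest reply is that a specific rule governs a general one. Criterion 13 names the drug and extends the ban to the whole study, so it is not merely a screening condition. Every site must read it to enrol a patient. The clause in 8.7.1 speaks only of unnamed other drugs. On this reading rosuvastatin is simply prohibited.

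Appendix I does not contradict that. Its title covers both disallowed and caution drugs, its introduction says it adds to the arm-level prohibitions, and it describes itself as not exhaustive. Listing rosuvastatin there is compatible with a ban, and leaving atorvastatin out of the BCRP table proves little. The BCRP bullet does not itself refer the reader to Appendix I. There are also general safeguards: patients must consult the Investigator before taking any medicine, concomitant drugs are recorded, and the causality guidance in Appendix H asks about other drugs.

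Much of this stands. A reader might infer that 8.7.1 permits rosuvastatin outright, so that the drug is both forbidden and allowed. The documents do not support that: no passage permits it by name, and permission arises only by combining 8.7.1 with Appendix I and overlooking criterion 13. Nor does 8.7.1 ban atorvastatin alone, since its CYP3A4 bullet also bans simvastatin and lovastatin.

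The reply does not remove the problem. The section headed for prohibited medication discusses the very mechanism behind the ban, names a different statin, and gives a weaker rule for the remainder without mentioning or referring to the ban.

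**Conclusion.** The inconsistency is real and sits in current, unredacted text. Criterion 13 prohibits rosuvastatin on BCRP grounds; the BCRP bullet of 8.7.1 prohibits atorvastatin and puts other BCRP-mediated drugs under caution; Appendix I makes rosuvastatin one of those other drugs. A site relying on the last two could treat as caution a drug that the first forbids. It should be corrected because it touches safety and the coding of deviations, but it is a matter of harmonising text and does not affect the design.

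Two further inferences go beyond the documents:

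- **That rosuvastatin is the likely replacement when a banned statin is stopped.** The protocol says nothing about switching statins and does not claim to list them all.
- **That a definite number of patients is affected.** The protocol gives no rate of statin use. Assuming 20% to 40% of the 20 patients planned for Arm B would give 0.20 × 20 = 4 to 0.40 × 20 = 8, but those would be statin users, not patients given rosuvastatin, and still less patients harmed or with toxicity wrongly attributed to study drug.

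No patient count is therefore claimed, and no effect on the objective response rate, sample size or interim decision is shown.

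**What to change.** Reconcile criterion 13 (Appendix B 4.2), the CYP3A4 and BCRP bullets of Appendix B 8.7.1, and the BCRP table of Appendix I, so that each named statin has one status and one stated reason (CYP3A4 or BCRP). State the result in 8.7.1, and mark the rosuvastatin entry in Appendix I to match. Which status applies to rosuvastatin is a clinical pharmacology decision for the sponsor and is not proposed here.

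The cost is about two lines of protocol text. Sample size, endpoints and analyses are unchanged.
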